Activation task: (3:00 min) developed by Hariri and colleagues to focus subject’s attention on the negative facial emotion depicted reliably activates the amygdale and limbic regions⁶⁸. A number of studies have reported altered activation of the limbic regions using this task. Increased limbic activation in BD has been reported with this task⁸⁴ and with other tasks using sad faces⁸⁵. We are currently using this task as well as the Go-NoGo task in ongoing studies and have considerable experience administering and analyzing the results. Each trial consists of a presentation of three faces depicting a negative emotion in which the subject

has to match the top picture with one of the two bottom pictures. In the control task oval shapes are used instead of faces. Five trials are presented in 22.5 sec long blocks, with three face presentation blocks interspersed with four shape blocks. Subject's task performance (accuracy, response times) will be compared between groups and considered for use in the correlation analyses or as covariates.

Emotional Go-NoGo task combines presentations of nonemotional (letter) and emotional (sad or happy) faces. This task tests emotion regulation and previous studies in BD have reported abnormal anterior cingulate activation⁸⁶. In the nonemotional task, subjects view a series of 12 letters presented in an 18 sec time period and respond to each letter (Go blocks) or to every letter except "X" (No-Go blocks). In the emotional task, subjects view happy and sad faces and press a response button for all faces (Go blocks) or specifically for happy or sad faces (No-Go blocks). Go and No-Go blocks of each category are repeated twice with the order of emotional and nonemotional blocks randomized within a 4:57 min scan. Subject and accuracy and response times compared across Go and No-Go conditions and disease states.

2c(ii)H2. Image Analyses: All analysis will be done blind to the subject's group status by trained analysts and inter-rater reliability will be obtained with a senior co-investigator([name])

a) Resting state functional connectivity (LFBF correlation): The time series data pre-processing (physiologic noise reduction, slice-timing correction, realignment, de-trending and bandpass filtering to extract low frequency BOLD fluctuations) will be accomplished using the AFNI software⁸⁷. SPM's (Wellcome Department of Cognitive Neurology, London, United Kingdom) mutual information algorithm will be applied to co-register each subject's high-resolution MPRAGE anatomical image to the mean of all functional connectivity image volumes and segment it into its tissue components. Three mean time-series, calculated by averaging across all brain, white matter and cerebrospinal fluid voxels will be utilized to account for any remaining global effects from each voxel's time series⁸⁸. The measures of functional connectivity will be evaluated on the AFNI pre-processed native-space connectivity volumes. We will either extract correlations between the mean time series of seed regions such as the amygdala and mean time series of another region such as the ventral anterior cingulate or calculate these correlations for all other voxels in the brain and thus generate connectivity maps. The more detailed description of the Pearson correlation coefficient calculation between the averaged LFBF time series of a-priori defined ROIs and its transformation to T-statistic was provided earlier⁴¹. Based on ACC region of the Talairach Daemon⁸⁹, ventral ACC (vACC) is defined as the rostral ventral part of the ACC resembling rostral Brodmann Areas (BA) 24 and 32, the area that has recently been reported to be involved in corticoamygdalar connectivity and mood regulation^{90,91}. The amygdalar ROIs will be defined using MarsBar's Montreal Neurological Institute (MNI) anatomical library definition but 10 mm diameter spherical regions centered at location (-23, -5, -15) and (23, -5, -15) will also be evaluated as adopted from the Talairach Daemon dataset⁸⁹. The medial and lateral OFC ROIs will also be defined from the MarsBar MNI anatomical library. The connectivity map approach used in our preliminary data analyses provides not only a measure of the regional connectivity but also its spatial distribution and can be utilized to fine-tune the seed region location, shape and size. These connectivity maps will be normalized to a common space by applying segmentation-generated transformation matrix, interpolated to 2 mm per side isotropic voxels and smoothed by a 6 mm full-width half-maximum (FWHM) Gaussian kernel. The resulting connectivity maps will be entered into SPM's second-level models (full factorial or paired-T design) to visualize as well as quantitate between-group differences. It should be noted that seed regions will be defined in the MNI space but that native-space ROIs will be checked using SPM's check-registration feature by overlaying them onto each subject's high-resolution anatomical and functional connectivity volumes. This procedure will detect low signal regions and normalization problems. Beside the above ROI seed based hypothesis driven analysis we will also explore other potential methods to conduct pattern analysis using independent and principal components analysis^{74,92}.

b) Regional Activation Analysis: Functional image volumes in NoGo-Go task will be processed using SPM standard individual first level modeling. Group effects will be obtained using a second level analysis within SPM. Furthermore, a priori defined ROIs will be used to extract mean activation effects for between-group statistical analyses and to collect ROI percent signal change in response to various emotional and non-emotional NoGo-Go conditions. The primary contrast for analysis would be Happy NoGo-Go and Sad NoGo-Go compared to letter NoGo-Go to measure regional brain activation specifically for response inhibition to emotional stimuli. Corrections for multiple comparison/multiple hypothesis will be performed using the false discovery rates⁹³.

c) Volumetric Analysis: While structural analysis is not part of the aims of this proposal we will conduct structural analysis on the high-resolution anatomical scan to explore correlations with functional measures of activation and connectivity. A semiautomated cortical reconstruction and volumetric segmentation will be

performed as previously reported by the investigators⁹⁴ with the Freesurfer image analysis suite⁹⁵. This process generates individual regional measures for cortical and subcortical anatomic structures. We will register individual maps to a standardized atlas and will apply a GLM approach to compare morphometric features across individual subjects and between study groups.

2c(ii)la. Statistical Analysis:

Specific Aim 1: Differentiation between BDD and UD: We will conduct a one way ANOVA with the connectivity and activation measures as dependent variables to look at differences between groups (BDD and UD). The analyses will be similar to those in our previous studies^{41, 42}. The normality assumptions will be examined using the Kolmogorov-Smirnov test. Box-Cox type transformation methods will be employed if the normality assumption is violated for the outcome variable. To adjust for multiple comparisons accounting for multiple brain ROIs and ad-hoc comparisons conducted within an ANOVA model, Bonferroni adjustment will be used to control overall type I error rates (over-all significance level will be set to 0.05). A post ANOVA logistic regression based classification model will be constructed to build a classifier between BDD and UD. Specificity and sensitivity will be examined using receiver operating characteristics (ROC) curves. We will use leave-one out cross validation method to assess predictive performance of our classification model⁹⁶.

Specific Aim 2: Differentiation between BDD, HRUD, LRUD and healthy control: We will use corticoamygdalar connectivity, amygdalar-LOFC connectivity and ACC Activation in Emotion to perform one-way ANOVA among all four groups. Prior to the analysis, each of these variables will be transformed (using the Box-Cox transformation) so that they will made as close to Gaussian as possible. The normality assumptions will be examined using the Kolmogorov-Smirnov test. Specificity and sensitivity will be examined as in Aim 1.

Specific Aim 3: Identification of imaging measures significantly affecting the rate of conversion from UD to BD: The conversion of UD subjects into BDD is defined as the time to event phenomenon and will be modeled using Cox-proportional hazard model given by,

$$\log(h(t)) = h_0(t) + \beta_1 X_1 + \beta_2 X_2 + \dots + \beta_p X_p$$

where $h(t)$ is the hazard or rate of conversion at time (t), $h_0(t)$ is the baseline conversion rate and X_i for $i = 1, 2, \dots, p$ are covariates. The subjects will be followed in the fashion described in Table 3 with periodic assessments. The assumption of constant relative hazard rate over time will be tested and remedied if required following data transformation or by incorporating a piecewise constant hazard model. Based on this framework, we will test the significance of imaging and activation measures on the hazard rate. Our primary objective here is to identify those covariates that significantly affecting the hazard rate. The grouping of the UD (HRUD and LRUD) will be also treated as a separate covariate and put in the model as an indicator variable. To detect the progression of disease severity (episodes of (sub) threshold hypo(mania)) we will additionally use Young Mania Rating Scale (YMRS) and the mania syndrome checklist from the Schedule for Depression and Schizophrenia (MSC-SADS) between study visits over during follow-up. We will test the group difference between LRUD and HRUD using mixed-effects linear regression analyses⁹⁷ with repeated measurements taken over two years. Each model will include a random intercept and slope and fixed effects group, and time, as well as the stratification covariates. A likelihood ratio test will examine the incremental contribution of the group effect over time.

Adjusting for covariates: These include behavioral rating such as, attentional variables such as response time, and accuracy of response, and changes in physiological ratings; demographic variables such as age, gender, and ethnicity; scores on behavioral measures such as anxiety; treatment with concomitant medications such as atypical neuroleptics during the study; treatment history, substance abuse, and trauma history; and structural variables such as whole brain and ROI volumes. We will first identify the covariates with highly correlated with the outcome measures. Next, from this pool of highly correlated covariates to guard against multicollinearity and to conserve for degrees of freedom to ensure that we have sufficient power. To control for potential confounding effects from these covariates and not over-fit in any of our models, we will use the forward stepwise regression model building approach - so that only one covariate will be included at a time in the model - which allows us to screen out covariates that are not related to our outcome measures by using an elevated p-value ($p=0.1$) and reserve statistical power to a limited number of variables that are shown to be associated with outcome measures in our data⁹⁸.

2c(ii)lb. Sample size and power consideration: Preliminary data obtained from BDD and UD subjects were compared with healthy subjects to obtain estimates of sample size at significance level set at 0.05. Proc Power of SAS software is used to estimate the sample size.

Specific Aim 1: We used our pilot data for Left LOFC-amygdala connectivity measure. This data yielded an effect size of 0.27 for difference between BDD and UD group. 40 samples in the BDD and 120 samples in UD group will give us more than 80% power to detect an effect size as low as 0.15 for the difference in Left LOFC-amygdala connectivity between two groups. Probability of type 1 error (alpha) was set always at 0.05. For ACC-left amygdalar connectivity measure, the effect size is 0.482. With previous mentioned sample size for each group we will have 90% power to detect an effect size as low as 0.3. Similar conclusion can be made for ACC activation in NoGo-Go task for which the data yielded an effect size of 0.726 for difference between BDD and UD group. Our proposed sample size is enough to detect the difference of effects with a power close to 90% at a significance level of 0.05. Even with 20% attrition rate (i.e. 32 BDD and 96 MDD) this sample size is large enough to ensure 80% power at alpha 0.05.

Specific Aim 2: For comparisons among BDD, HRUD, LRUD and healthy subjects all three connectivity and activation measures produce power more than 80% for 40 subject per group to detect a significant difference. In the present case with 40 BDD, 60HRUD and 60 LRUD samples the power calculation is little involved, nevertheless increased sample size ensures more than 80% power at alpha= 0.05. To compare HRUD vs. LRUD left LOFC-amygdala connectivity measure yields an effect size of -0.254. For 60 subjects/group this produces 88% power at alpha 0.05.

Specific Aim 3: Using a conservative assessment of a 6% conversion rate for the LRUD group and 14% conversion rate for HRUD group, we calculate that with a sample size of 60 per group (HRUD and LRUD) we will have 80% power with type I error fixed at 0.05, under the assumption of 20% attrition rate in both groups, to detect statistically significant imaging measures as well as differential rate of conversion. We have used Bacsafra's⁹⁶ web based program to arrive at this power calculation. For sample size requirement to differentiate between HRUD and LRUD subjects via MSC-SAD and YMRS score peak-change and slope of change we will compare the mean baseline score and the mean peak scores using two sample t-test. Peak value for each group are extrapolated from usual values seen for YMRS iduring hypomania. Under the assumption of homogeneity among groups, for both the scales a sample of size 60 will be adequate even after adjusting for 20% attrition is adequate to ensure 90% power at alpha 0.05.

[figure not shown]

Fig. 8. Hypothetical YMRS peak score changes for HRUD and LRUD group over time

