connectivity besides the use of conventional fMRI regional activation paradigms of response to emotional stimuli. Preliminary findings (described below) from our studies support this hypothesis and provide rationale to conduct a definitive clinically relevant study.

2cii. Methods and Design:

We plan to recruit unmedicated 40 BDD, 60 HRUD, 60 LRUD as well as 40 HC subjects closely matched for age, gender and ethnicity for the study. We expect that at baseline 10% of subjects could be lost. During follow-up 15 - 20 % of HRUD and LRUD of patients may be lost before adequate data for development of (hypo)mania is collected. The number of subjects remaining will be adequate for statistical analysis proposed. For the exploratory aim, both the UD groups will be offered 24 months of antidepressant treatment with frequent mood assessments in the study. The other BDD and HC subjects will be followed up by phone for 24 months. During the 24 months all subjects will be rated on YMRS and the MSC-SADS for any periods suggestive of occurrence of hypomanic symptoms.

2c(ii)A. Human Subjects: The detailed inclusion and exclusion criteria and protection procedures are described in Human Subjects section E1a.

2c(ii)B. Recruitment and Timeline:

1. **Year 1:** Week 1 – 12: Training of study personnel and organization for initiation of study.
2. **Year 1 – Year 5:** Week 12 – Week 234: Recruitment of subjects and conduct of the study.
3. **Year 5:** Week 234 – Week 260: Continued follow-up of subjects and final data analysis and publication.

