E2b7. Treatment and Referral after the study: While the BD subjects is being screened and the fMRI scan being arranged and for the UD patients when they are coming to the end of the 24 months supervised treatment, we will start the process of identifying with the patients where they would like to be referred for treatment. A range of treatment options are available in the Indianapolis area including private university and other outpatient clinics and state hospital. We already have a handout available for all the addresses and phone numbers for patient to make an appointment which we routinely give to our research subjects after they finish the study with us. In this study, we will additionally call up the treater of the patient's choice and make sure that subjects will have an appointment. UD subjects will still be followed up every 3 months until the end of the study. As the patients included in this study will present as unmedicated because either they have never been diagnosed before or for some other reason elected not to take medication that was recommended (not an uncommon situation for many young patients) this process will help in patient complying and following through with treatment. In this way we will be able to get patients engaged in treatment which otherwise they are unlikely to get on their own.

E2b8. Loss of confidentiality: Documents which contain patient-identifying data will be kept in locked filing cabinets, with access restricted to authorized investigators participating in the research, and secretarial and administrative personnel who have been informed about the requirement to maintain confidentiality. Computer records that contain patient identifying data will be secured by passwords. Patients will not be identified in any reports or publications that may result from this study. University policies regarding HIPAA regulations for research subjects will be followed.

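### If recruitment runs to week 234, subjects enrolled after week 156 cannot complete 24 months by week 260, and the 20% attrition in the Aim 3 power leaves out the expected 10% baseline loss

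*Combined protocol and SAP*

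**What the plan says.** Section 2c(ii)B (Recruitment and Timeline) gives "Week 12 – Week 234: Recruitment of subjects and conduct of the study", followed by "Week 234 – Week 260: Continued follow-up of subjects and final data analysis and publication". Recruitment and conduct share one window, and no separate date for the end of recruitment appears anywhere.

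Section 2cii (Methods and Design) states that "both the UD groups will be offered 24 months of antidepressant treatment with frequent mood assessments in the study". The Aim 3 analysis of mania ratings is a mixed model on "repeated measurements taken over two years", and Table 3 runs to month 24. Section E2b7, however, adds that after the supervised treatment "UD subjects will still be followed up every 3 months until the end of the study". The end of the study is not defined there.

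On losses, section 2cii says "We expect that at baseline 10% of subjects could be lost" and then expects a further 15-20% of HRUD and LRUD subjects to be lost in follow-up. The Aim 3 paragraph of section 2c(ii)lb claims 80% power with 60 per group, conversion of 6% against 14% and alpha 0.05, "under the assumption of 20% attrition rate in both groups". It gives no time unit for the two rates and does not mention the baseline loss. The same paragraph compares peak scores with a two-sample t-test.

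**The concern.** Twenty-four months is 104 weeks, and only 26 weeks separate the end of the recruitment-and-conduct window from study closure. Late enrolees would therefore have less follow-up than Aim 3 assumes, and the plan has no rule for them. Shorter follow-up means fewer conversions and less information on slopes. It also means systematically lower peaks, because a maximum taken over 6 months is not comparable with one taken over 24. If HRUD and LRUD subjects are recruited at different speeds, that last effect would bias the comparison between the groups.

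The attrition figure compounds this: 20% matches only the upper end of the expected follow-up loss. A reader of the power section would expect two-year data on 48 subjects per group, and the plan's own figures do not give that. The offer of 24 months of treatment (sections 2cii and E3) also has to be reconciled with the timeline for late enrolees.

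**Working it through.** **Plan's own figure first.** Read 6% and 14% as cumulative 24-month rates with constant hazards. Then HR = ln(0.86)/ln(0.94) = 2.44 and ln HR = 0.891.

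- Events needed for 80% power, two-sided 0.05 (Schoenfeld, 1:1): 4 × (1.960 + 0.842)² / 0.891² ≈ 40.
- Events expected with 20% attrition and full follow-up: 48 × (0.06 + 0.14) = 9.6.
- Power = Φ(√(9.6/4) × 0.891 − 1.960) = Φ(−0.58) = 28%.

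If the rates are annual, the 24-month rates are 1 − 0.94² = 11.6% and 1 − 0.86² = 26.0%. That gives 18.1 events and 47% power. A two-proportion test gives 25% and 44%. One-sided power on the two methods is 37-40% and 56-60%. The stated 80% is not reproduced.

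**Timeline.** The last entry with full follow-up is 260 − 104 = week 156. The last possible entry gets 260 − 234 = 26 weeks. Assume uniform accrual over weeks 12-234:

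- share unable to complete: (234 − 156)/(234 − 12) = 78/222 = 35%, about 42 of 120 UD subjects;
- mean available follow-up, capped at 104 weeks: (144 × 104 + 78 × 65)/222 = 90.3 weeks;
- mean available follow-up, uncapped to week 260: (248 + 26)/2 = 137 weeks.

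**Attrition.** 60 × 0.90 × 0.85 = 45.9 and 60 × 0.90 × 0.80 = 43.2 per group, against 60 × 0.80 = 48. Total loss is 23.5-28%.

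**Both together.** Per group, events = n × mean of [1 − exp(−λf)], with λ = −ln(1 − p₂₄)/104, where p₂₄ is the 24-month rate and f is each subject's available follow-up. Capped at 104 weeks, the mean conversion probabilities are 0.0522 and 0.1222 (24-month rates), or 0.1015 and 0.2287 (annual rates). At n = 43.2 this gives 43.2 × 0.1744 = 7.5 events, or 43.2 × 0.3302 = 14.3 events.

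That treats every dropout as contributing nothing. A milder version starts from 54 per group after the baseline loss and lets dropout act as a constant hazard μ = −ln(0.80)/104 alongside truncation. Each subject then contributes λ/(λ+μ) × [1 − exp(−(λ+μ)f)], which gives 8.5 or 16.2 events.

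| Scenario | 24-month rates: events, power | Annual rates: events, power |
|---|---|---|
| 48 per group, full 24 months | 9.6, 28% | 18.1, 47% |
| 23.5-28% loss, censored at week 260, capped at 24 months | 7.5-8.5, 23-26% | 14.3-16.2, 39-43% |
| 23.5-28% loss, followed to week 260 without cap | 11-12, 31-33% | 20-21, 51-54% |

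Power is two-sided Schoenfeld throughout. In the capped row, the lower end removes all dropouts at 28% total loss, and the upper end is the milder version with 20% follow-up dropout.

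**The case against.** The strongest case against has five parts.

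1. **The window is combined.** It covers recruitment and conduct, so recruitment to week 234 is a reading of the text. That stands, and the point is conditional on it. It remains the natural reading, since follow-up is described as merely continuing only from week 234.
2. **The main models tolerate unequal follow-up.** Cox regression accepts administrative censoring, and mixed models with random intercept and slope accept unequal follow-up. This stands: the cost is events and precision, not validity. It does not rescue the t-test on peak change.
3. **Section E2b7 may provide longer follow-up.** If observation to the end of the study is analysed through week 260, early enrolees more than make up for late ones and expected events exceed 9.6. The two-year wording elsewhere points the other way, and the documents do not settle it.
4. **The power program's inputs are unknown.** Section 2c(ii)lb cites a web-based program without its accrual or follow-up settings, so one cannot say that it treated everyone as complete. This also stands.
5. **Aim 3 is exploratory**, intended to inform later studies. That limits how much weight the point should carry.

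Three stronger conclusions might be inferred, and the documents do not support them. The first is that the timeline defeats two-year follow-up altogether; under uniform accrual about 65% can still complete. The second is that truncation and attrition explain the distance from 80% to 23%; on 24-month rates, 52 of those 57 points are present with full follow-up and 20% attrition. The third is that enrolment must stop at week 156. That would leave no time for analysis before week 260, and it would cut the recruitment window from 222 to 144 weeks for Aims 1 and 2, which rest on baseline scans.

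**Conclusion.** The point holds in a limited form. The plan states neither a recruitment end nor a censoring rule that would reconcile 24 months of follow-up with closure at week 260, and its Aim 3 attrition contradicts its own expected losses. With follow-up capped at 24 months, the joint cost is about 3-8 points of two-sided Schoenfeld power: 28% to 23-26% on 24-month rates, 47% to 39-43% on annual rates. With observation to week 260, power would rise to 31-33% or 51-54%. The stated 80% is not reached on any of these readings. Most of that shortfall is separate from timeline and attrition: 52 points on 24-month rates and 33 on annual rates.

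These figures assume uniform accrual to week 234, constant hazards and equal truncation in both groups. Values near 80% appear only if the rates are taken as per six months, which nothing in the documents supports. The attrition point concerns Aim 3 only: Aim 1 allows 20% loss, which covers the 10% expected at baseline.

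**What to change.** Keep the timeline and make four changes to the text.

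1. State that Aim 3 has variable follow-up with administrative censoring: about 6-24 months, or to week 260 if that is what section E2b7 means. Make section E2b7, Table 3 and the two-year wording agree, and reconcile the 24-month treatment offer with the closing date.
2. Give the time unit of the 6% and 14% conversion rates.
3. Replace the 80% figure with expected events and power computed under that follow-up and 23.5-28% total loss, stating the accrual assumption and the sidedness of alpha.
4. Replace the two-sample t-test on peak change with an analysis that accounts for each subject's observation time, for example the peak within a common window that all subjects reach (26 weeks if recruitment runs to week 234) or adjustment for follow-up length.

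The planned Cox and mixed models can stay, and no recruitment cut-off at week 156 is needed. The cost is rewording and recalculation, plus a less favourable stated power for an exploratory aim. A 26-week common window would also discard later peaks, which is a reason to consider adjustment instead.
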